### 12.1.2.3 Medical History

All relevant medical and surgical history and current medical conditions will be recorded at the Screening Visit (Visit 1).

Medical history data will be listed by treatment and subject.

### 12.1.2.4 Extent of Exposure

The number of subjects exposed to each study treatment will be summarized.

The number of days on treatment and the number of days on study will be summarized by study treatment.

Treatment compliance will be calculated as follows:

Compliance = (the total number of doses actually taken) / (total number of doses scheduled)\*100 where:

For subjects who have completed the study, the total number of doses scheduled is 728 (2\*7\*52=728, [REDACTED] for 52 weeks).

For subjects whose participation is terminated early, compliance will be determined from their duration in the study, up to the time they are considered early terminated. The total number of doses scheduled = the minimum between 728 and [(Date of Discontinuation – Date of First Application + 1)\*2].

Subjects taking fewer than 75% or more than 125% of the required doses will be considered non-compliant with dosing.

In addition, treatment compliance will be classified into four categories (less than 75%, 75% to 100%, greater than 100% to 125%, and greater than 125%). Treatment compliance will be summarized by categories and study treatment.

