10.1.1 Administration

Each nasal spray bottle contains [REDACTED]. At the Screening Visit (Visit 1), site personnel will adequately train the subjects on the proper use of the NS bottle ([Appendix 2](#)). At each subsequent visit, site personnel will review instructions on the proper use of the NS bottle with the subject and prime the NS bottle as needed. The priming process must be completed in such a way as to avoid any possible inhalation and contamination by the subject.

Each subject will be provided with single-blind, placebo, run-in medication (GSP 301 placebo NS pH [REDACTED]) for use until the Randomization Visit (Visit 2). Subjects will self-administer the first dose of the single-blind GSP 301 placebo NS pH [REDACTED] in the presence of the Investigator or designee during the Screening Visit (Visit 1). Subjects should be instructed NOT to administer the single-blind study medication on the day of the Randomization Visit (Visit 2).

At the Randomization Visit (Visit 2), each subject will be provided with double-blind study medication according to the randomization scheme. The site personnel will review instructions on the proper use of the NS bottle with the subject and prime the NS bottle as needed. The priming process must be completed in such a way as to avoid any possible inhalation and contamination by the subject. The first dose of double-blind study medication (AM dose on Day 1) will be self-administered in the clinic in the presence of the Investigator or designee during the Randomization Visit (Visit 2). All subsequent doses will be administered at home. The last scheduled dose will be the [REDACTED] on the day before the Final Visit/Discontinuation Visit (Visit 12). Study medication should not be taken (either at home or at the clinic) on the morning of the Final Visit/Discontinuation Visit (Visit 12).

Detailed instructions for the proper use of the treatment NS devices are provided in [Appendix 2](#).

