11.12 Final Visit: Visit 12 (Week 52 + 10 Days)

The following procedures and evaluations will be performed at this visit:

1. Distribution of RQLQ(S), review instructions with the subject, and subject completion of RQLQ(S). This must be the first procedure performed.

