### **Per Protocol Set (PPS)**

The Per Protocol Set (PPS) will consist of the subset of the FAS who do not meet criteria for PPS exclusion. These criteria are to capture relevant non-adherence to the protocol (defined as a 'major deviation', especially those that affect interpretation of the AM rTNSS endpoint). The PPS will be a secondary analysis set for the efficacy analysis (except for RQLQ(S)). The PPS will be used to assess the robustness of the results from the statistical tests based on the FAS.

Major deviations will lead to the exclusion of a subject from the PPS. Major protocol deviations will be identified during the Blinded Data Review Meeting (BDRM) before database lock.

Major protocol deviations *may* include:

- Subjects who had their blinded randomization code broken.
- Subjects with overall treatment compliance <75% or >125%.
- Subjects who used prohibited medications (prior and/or concomitant) that may have significant influence on efficacy.
- Subjects who did not satisfy the inclusion/exclusion that may have significant influence on efficacy.
- Subjects not treated with the treatment assigned at randomization, but wrongly treated in another treatment group.

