| Week 6  | GSP 301 placebo NS pH [REDACTED] (N=xxx) | xxx                    | xxx.xx | xxx.xx         |  |                    |               |         |
|         | GSP 301 NS (N=xxx)                       | xxx                    | xxx.xx | xxx.xx         | xxx.xx                                 | xxx.xx             | xx.xx – xx.xx | x.xxxx  |
| Week 30 | GSP 301 placebo NS pH [REDACTED] (N=xxx) | xxx                    | xxx.xx | xxx.xx         |  |                    |               |         |
|         | GSP 301 NS (N=xxx)                       | xxx                    | xxx.xx | xxx.xx         | xxx.xx                                 | xxx.xx             | xx.xx – xx.xx | x.xxxx  |
| Week 52 | GSP 301 placebo NS pH [REDACTED] (N=xxx) | xxx                    | xxx.xx | xxx.xx         |  |                    |               |         |
|         | GSP 301 NS (N=xxx)                       | xxx                    | xxx.xx | xxx.xx         | xxx.xx                                 | xxx.xx             | xx.x – xx.x   | x.xxxx  |

Baseline is defined as the domain score at the randomization visit.

n: Number of subjects with data available in the specific treatment group

LSMeans: Least square means; Std Err LSMean: Standard error of the LSMean

LSMeans, Std Err of LSMean, 95% confidence intervals and p-values are based on mixed model repeated measures model with change from baseline as dependent variable, treatment group and site as fixed effect, baseline as covariate, week as the within-subject effect and week-by-treatment interaction.

Programming note: the interaction terms treatment\*baseline and treatment\*site will only be included in the footnote if significant in the model

Programming notes: table will continue for other domains

Data source: xx

Created on: ddmmyy hh:mm

Page 1 of N

|  |                                    |                                  |
|--|------------------------------------|----------------------------------|
| Protocol Number:
GPL/CT/2014/018/III
(Study No. GSP 301-303) | SAP Version Number:
Version 1.0 | SAP Version Date:
04-Apr-2017 |
|--|------------------------------------|----------------------------------|

**L16.2.1 Listing of Subject Disposition  
(Safety Analysis Set)**

| Treatment Group                  | Subject / Randomization Number | Date of Last Dose Taken | Date of Completion/ Early Termination/ Withdrawal | Reason for Early Termination/ Withdrawal |

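### The compliance denominator in SAP 12.1.2.4 does not follow the protocol's dosing period, so fully adherent subjects can score above 100% (late completers) or below 75% (early terminators with a lag before termination)

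*SAP*

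**What the plan says.** SAP 12.1.2.4 defines compliance as doses taken over doses scheduled, with two denominators.

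- Completers: "For subjects who have completed the study, the total number of doses scheduled is 728", whatever the actual date of Visit 12.
- Early terminators: "compliance will be determined from their duration in the study, up to the time they are considered early terminated". The formula is "the minimum between 728 and [(Date of Discontinuation – Date of First Application + 1"), with the day count doubled. Date of Discontinuation is not defined.

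The same section adds: "Subjects taking fewer than 75% or more than 125% of the required doses will be considered non-compliant with dosing". Among the deviations that may count as major, the PPS definition in SAP 10.0 lists "Subjects with overall treatment compliance <75% or >125"%. Major deviations lead to exclusion from the PPS and are identified at the blinded data review meeting.

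On dosing, Protocol 10.1.1 puts the last scheduled dose on the day before the final or discontinuation visit and states: "Study medication should not be taken (either at home or at the clinic) on the morning of the Final Visit/Discontinuation Visit (Visit 12"). SAP 5.0 and note d of SAP Appendix 2 also place the last dose on the day before. The Visit 12 window is given in two ways: "11.12 Final Visit: Visit 12 (Week 52 + 10 Days") in the Protocol text, and Day 365±10 in Protocol Appendix 1.

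**The concern.** A compliance figure should return 100% for someone who took every dose that was due. This one does so only in special cases.

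For completers, dosing follows the actual visit date while the denominator stays at 728.

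For early terminators there are two mismatches. The +1 schedules two doses on the discontinuation day, when the last dose was already taken the day before. In addition, the reference to duration in the study carries the denominator on to the termination date, even if the drug was stopped earlier or the last returned diary ended earlier. The documents expect such gaps. Protocol 9.4 describes subjects who stop treatment and later return for end-of-study assessments, and SAP listing L16.2.1 holds "Date of Last Dose Taken" separately from the termination date.

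What is at stake is the accuracy of the compliance table (T14.1.9.11.1) and the figure used to screen subjects for the PPS, the set meant to show how robust the FAS efficacy results are.

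**Working it through.** Inputs:

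- Two doses a day for 52 weeks; limits of 75% and 125% (SAP 12.1.2.4).
- First double-blind dose on the morning of Day 1; last dose on the day before the final or discontinuation visit (Protocol 10.1.1). Which of that day's doses is last is blacked out; I assume the second.
- Visit days 22, 43, 85, 127, 169, 211 and 365±10 (Protocol Appendix 1).

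**1. The plan's own figure.** 2 × 7 × 52 = 728. Two doses on each of Days 1 to 364 also gives 728, so the constant is exact for Visit 12 on Day 365.

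**2. Completers.** With perfect use and Visit 12 on Day V, the SAP gives 2(V − 1)/728.

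| Visit 12 | Doses | SAP compliance |
|---|---|---|
| Day 355 | 708 | 97.3% |
| Day 365 | 728 | 100.0% |
| Day 366 | 730 | 100.3% |
| Day 370 | 738 | 101.4% |
| Day 375 | 748 | 102.7% |

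If the last dose were the morning dose of the previous day, Day 366 would still give 729/728 = 100.1%. Exceeding 125% needs V − 1 > 455, that is Day 457 or later, far outside either window.

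**3. The extra day for early terminators.** With the last dose on the day before discontinuation day D, the SAP gives 2(D − 1)/(2D): Day 3, 4/6 = 66.7%; Day 4, 6/8 = 75.0% (not below the limit); Day 43, 84/86 = 97.7%. On its own, this error takes a subject below 75% only by Day 3.

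**4. The lag.** With perfect use through Day L and a discontinuation date g days later, the SAP gives 2L/min(728, 2(L + g)). Below the cap, L/(L + g) < 0.75 is the same as g > L/3.

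| L | First whole-day lag giving <75% |
|---|---|
| 14 | 5 days |
| 28 | 10 days |
| 42 | 15 days |
| 84 | 29 days |
| 126 | 43 days |

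At the cap, 2L/728 is at least 0.75 when L is at least 273, so the limit cannot be crossed from there on.

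Last dose on one visit day and termination on the next:

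| Last dose → termination | SAP compliance |
|---|---|
| Day 22 → 43 | 44/86 = 51.2% |
| Day 43 → 85 | 86/170 = 50.6% |
| Day 85 → 127 | 170/254 = 66.9% |
| Day 127 → 169 | 254/338 = 75.1% |
| Day 169 → 211 | 338/422 = 80.1% |

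**5. Unreturned diary.** Adherence is monitored from the diary (Protocol 10.1.2), and L16.2.5.2 lists confirmed doses by diary, so I take the numerator to stop at the last returned diary. A diary returned at Day 127 confirms 126 × 2 = 252 doses; termination on Day 190 (an assumed date) gives 252/380 = 66.3%. A diary returned at Day 169 confirms 336; termination on Day 211 gives 336/422 = 79.6%, not flagged. The result depends on the lag.

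**The case against.** The case against is substantial. The constant 728 is correct for the nominal schedule. Date of Discontinuation is undefined; if it means the date the drug was stopped, most of the early-terminator problem disappears. The PPS list says only what major deviations may include, and the blinded meeting can see last-dose and termination dates side by side. Interpretation rests on the FAS, efficacy is a secondary objective, and the safety set is untouched. Counting undosed study time as non-adherence is also defensible: a subject who simply stops spraying but stays in the study should not score 100%.

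Most of this stands and limits the point. It does not remove it. The sentence before the formula ties the period to time in the study, so the termination date is the more natural reading. The meeting would start from a distorted figure. The argument about undosed time applies to days on which the drug was still due, not to days after it was stopped or after the diary record ended.

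A reader might infer more than the documents support:

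- That flagged subjects are removed from the PPS automatically. The list is permissive and settled at blinded review.
- That the rule selects the PPS on outcome. Nothing shows longer lags after adverse events or lack of efficacy, and Protocol 9.4 and 11.13 call for discontinuation procedures, which would tend to shorten them. Loss to follow-up is the plausible source of long gaps.
- That about half the subjects are affected, because 50% attrition is expected by 52 weeks. That is the share to whom the formula would apply, not the share with a long enough lag.
- That late completers are treated as over-users. The SAP regards 75% to 125% as compliant.

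**Conclusion.** The point holds in a limited form and should be corrected before database lock.

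For fully adherent completers the error runs from −2.7 to +2.7 percentage points across Days 355 to 375. Those seen on Days 366 to 375 fall in the row for more than 100% up to 125%. This is a tabulation error only, with no PPS effect, and two missed doses bring a Day 366 completer back to 100% (20 do so at Day 375).

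For early terminators the extra day is trivial after the first few days. The lag is what matters: more than L/3 days takes a fully adherent subject below 75%, for L up to 272. This can flag the subject for possible PPS exclusion. The number affected cannot be estimated, because neither document gives lag times.

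The early-terminator conclusion assumes that Date of Discontinuation means study termination; the lack of a definition itself needs correcting. The unreturned-diary case also assumes a diary-based numerator. The primary safety analysis does not depend on any of this.

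**What to change.** In SAP 12.1.2.4:

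- **Completers:** scheduled doses = 2 × (Visit 12 date − first dose date). Drop the 728 constant. Day 375 then gives 748/748 = 100%.
- **Early terminators:** define Date of Discontinuation as the date study drug was stopped, by recorded decision or at the discontinuation visit, and schedule no doses on the day of that visit. A discontinuation visit on Day 3 then gives 4/4 = 100%. Drug stopped by recorded decision on Day 43, after that day's doses, gives 86/86 = 100% even if termination is on Day 85.
- **Non-use while still assigned to drug:** keep those days in the denominator. If the same subject simply stopped spraying after Day 43 and had a discontinuation visit on Day 85, the figure is 86/(2 × 84) = 51.2%, which is real non-adherence.
- **Diary not returned:** end numerator and denominator together at the last entry of the last returned diary, and flag the subject for the blinded review, since truncation could hide someone who abandoned drug and diary together.

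Reconcile the Visit 12 window between Protocol 11.12 and Appendix 1.

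The cost is SAP wording and a few lines of code. First-dose, last-dose, visit, termination and last-diary-entry dates are already in the planned listings (L16.2.1, L16.2.5.1 to L16.2.5.3). The documents do not show a separate field for the date of a decision to stop drug, so its source should be confirmed. Separating a recorded stop from self-directed non-use will need some judgement at the blinded review.

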### 12.1.2.5 Concomitant Medications

At Visit 1 subjects will be questioned about current and prior concomitant medication use. At other visits subjects will be questioned about ongoing or new concomitant medication use.

|   |   |   |
|---|---|---|
|  | STATISTICAL ANALYSIS PLAN          |   |
| Protocol Number:
GPL/CT/2014/018/III
(Study No. GSP 301-303)         | SAP Version Number:
Version 1.0 | SAP Version Date:
04-Apr-2017 |

Medications will be grouped and presented as follows:

- Prior medications: defined as medications that started and ended before the first administration of the study medication.
- Concomitant medications: defined as medications either ongoing or ended on or after the first dose of study medication.

All prior and concomitant medications taken since screening until the end of the study will be listed by treatment and subject.

- If the end date and 'ongoing' are missing then the medication will be considered as concomitant medication.
- In cases of partial end dates, the following conventions will be applied:
  - If the end day is missing, and the end month and year are not missing, the end day will be imputed using the last day of the month.
  - If the end day and month is missing, and the end year is not missing, the end day and month will be imputed using '31DEC'. If this leads to a date after the last visit date, then the last visit date will be used instead.
  - If the end date is completely missing, the end date will be imputed using the last visit date.
- The partial dates will be provided as such in the subject data listings (with the imputed dates).

## 12.2 Safety Analyses

### 12.2.1 Overview of Planned Safety Analyses

The safety analyses will be based on the SAS, unless otherwise specified.

[Table 2](#) provides an overview of the planned analyses.

|  |                                    |                                  |
|--|------------------------------------|----------------------------------|
| Protocol Number:
GPL/CT/2014/018/III
(Study No. GSP 301-303) | SAP Version Number:
Version 1.0 | SAP Version Date:
04-Apr-2017 |
|--|------------------------------------|----------------------------------|

**Table 2: Overview of Planned Safety Analyses**

| Display Type                    | Data Displays Generated |        |         |
|---------------------------------|-------------------------|--------|---------|
|                                 | Table                   | Figure | Listing |
| Adverse Events           |                         |        |         |
| Overview                        | Y[2]                    |        |         |
| Treatment Emergent AEs          | Y[1][2]                 |        | Y       |
| Treatment Emergent AEs Severity | Y[2]                    |        | Y       |
| Drug-Related AEs                | Y[2]                    |        | Y       |
| Placebo Run-In Period AEs       | Y[2]                    |        | Y       |
| AEs Leading to Withdrawal       |                         |        | Y       |
| SAEs                            | Y[2]                    |        | Y       |
| Treatment Emergent SAEs         | Y[2]                    |        | Y       |
| Laboratory               |                         |        |         |
| Biochemistry                    | Y[3] [2]                |        | Y       |
| Haematology                     | Y[3] [2]                |        | Y       |
| Urinalysis                      | Y[3] [2]                |        | Y       |
| Pregnancy Test Results          |                         |        | Y       |
| Other                    |                         |        |         |
| Vital Signs                     | Y[4] [2]                |        | Y       |
| ECGs                            | Y [5] [2]               |        | Y       |
| Physical Examination            | Y[6] [2]                |        | Y       |
| Focused ENT Examination         | Y[7] [2]                |        | Y       |

**NOTES :**

- Y = Yes display generated.
- [1]: Display will also be produced by SOC, severity, and by relationship to study medication
- [2]: Display will be based on safety analysis set
- [3]: Display will be produced separately for overall laboratory assessments (inc. change from baseline), change from baseline in laboratory results, and potentially clinically significant laboratory results, and shift tables
- [4]: Display will be produced separately for overall summary (inc. change from baseline), for potentially clinically significant results, and shift tables
- [5]: Display will be produced separately for overall summary (inc. change from baseline), change from baseline in ECG interpretation, and potentially clinical significant ECGs, and shift tables
- [6]: Display will be produced separately for overall summary, and for potentially clinically significant results
- [7]: Display will be produced separately for overall summary, and for

## STATISTICAL ANALYSIS PLAN

|  |                                    |                                  |
|--|------------------------------------|----------------------------------|
| Protocol Number:
GPL/CT/2014/018/III
(Study No. GSP 301-303) | SAP Version Number:
Version 1.0 | SAP Version Date:
04-Apr-2017 |
|--|------------------------------------|----------------------------------|

| Display Type | Data Displays Generated |        |         |
|--------------|-------------------------|--------|---------|
|              | Table                   | Figure | Listing |

potentially clinically significant results

### 12.2.2 Adverse Events

All AEs will be coded according to the current version of MedDRA (version 18.1 or later). Adverse events occurring between the subjects signing informed consent and administration of the first dose of the randomized study medication will be regarded as pre-treatment AEs and will be included in the subject listings but not in the summary tables. Adverse events occurring after the first dose of the randomized study medication will be defined as treatment-emergent adverse events (TEAEs) and will be listed and summarized by System Organ Class (SOC) and Preferred Term (PT).

The safety endpoints related to AEs are:

- Proportion of subjects with TEAEs.
- Proportion of subjects with treatment-related TEAEs.
- Incidence, type, and severity of the TEAEs after 30 weeks of study treatment.
- Incidence, type, and severity of the TEAEs after 52 weeks of study treatment.

Summaries of the number and percentage of subjects with TEAEs and the number of TEAEs experienced will be presented by treatment group. The number of subjects and the number of TEAEs will be presented using frequency counts and percentages, overall and by SOC and PT. The percentages will be calculated as the number of subjects with TEAEs divided by the number of subjects in the safety analysis set. Tables of the number and percentage of subjects and the number of TEAEs by intensity and by relationship to study medication will also be presented. Similar tables will be created for treatment related AEs. Events will be assigned to the study treatment administered prior to the start of the TEAE. Events that occurred during discharge and final follow-up will be assigned to the final treatment.

The number and percentage of subjects with a TEAE that has a start date within 30 weeks of the start of treatment ( $\leq 182$  days) will be summarized by severity and study treatment group, overall, and by SOC and PT using frequency counts and percentages. A similar summary will be produced including all TEAEs during the study (i.e., after 52 weeks of treatment).

The overall p-value of the comparison among three treatment groups by SOC and PT will be produced using Fisher's exact test for each SOC and PT as well as overall subjects with at least one TEAEs. .

|  |                                    |                                  |
|--|------------------------------------|----------------------------------|
| Protocol Number:
GPL/CT/2014/018/III
(Study No. GSP 301-303) | SAP Version Number:
Version 1.0 | SAP Version Date:
04-Apr-2017 |
|--|------------------------------------|----------------------------------|

Additionally, the number and percentage of AEs, SAEs, TEAEs leading to discontinuation, and TEAEs related to the IP will be summarized by SOC, PT, and study treatment group.

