12.4 Safety Assessments

Safety assessments will consist of monitoring and recording all AEs, (including severity as mild, moderate and severe as per [Section 12.4.1.2](#)), and SAEs; regular monitoring of hematology, biochemistry, and urinalysis values (as applicable per the protocol or for safety reasons); periodic measurement of vital signs and ECGs; and physical examinations as detailed in the Schedule of Procedures and Assessments ([Appendix 1](#)). Additional details on the safety procedures performed in the study are detailed below.

Any abnormal laboratory test result (hematology, biochemistry, or urinalysis) or other safety assessment (eg, 12-lead ECGs, radiological scans, vital signs measurements), including any that worsen from baseline, that is considered to be clinically significant in the medical and scientific judgment of the Investigator will be recorded as an AE or SAE.

However, any clinically significant safety assessment that is associated with the underlying disease, unless judged by the Investigator to be more severe than expected for the subject's condition, will not be reported as an AE or SAE.

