12.4.1 Adverse Events

The Investigator or site staff will be responsible for detecting, documenting, and reporting events that meet the definition of an AE or SAE.

The reference safety information for this study is the IB Section 6.4.8.2 Reference Safety Information within the Summary of Data and Guidance for Investigators.

12.4.1.1 *Adverse Events*

An AE is defined as any untoward medical occurrence in a subject administered IP that does not necessarily have a causal relationship with the treatment. An AE can, therefore, be any unfavorable and unintended sign (including an abnormal laboratory finding), symptom or disease (new or exacerbated) temporally associated with the use of an IP, whether or not related to the IP. An AE includes any event, regardless of the presumed causality between the event and the IP.

Events that, while not necessarily meeting the definition of AEs, should be treated as such because they may be reportable to Regulatory Authorities according to AE reporting regulations, whether or not considered causally associated with IP, include the following:

- IP overdose, whether accidental or intentional.
- IP abuse.
- An event occurring from IP withdrawal.
- Inadvertent or accidental IP exposure (e.g., product leaking or being spilled onto a subject or care-giver).
- Unexpected therapeutic or clinical benefit from the IP.
- Medication errors (i.e., incorrect route of administration, incorrect dosage, use of incorrect product).

Events that do not meet the definition of an AE include:

- Medical or surgical procedure (e.g., endoscopy, appendectomy); the condition that led to the procedure is an AE.
- Situations where an untoward medical occurrence did not occur (social and/or convenience admission to a hospital).
- Anticipated day-to-day fluctuations of pre-existing disease(s) or condition(s) present or detected at the start of the study that do not worsen.
- The disease/disorder being studied or expected progression, signs or symptoms of the disease/disorder being studied, unless more severe than expected for the subject's condition.

12.4.1.2 *Assessment of Severity of Adverse Events*

The severity of AEs is classified as follows:

- Mild: The AE is a transient discomfort and does not interfere in a significant manner with the subject.
 The AE resolves spontaneously or may require minimal therapeutic intervention.
- Moderate: The AE produces limited impairment of function and may require therapeutic intervention.

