13.7.2 Adverse Events

Adverse events will be coded using the current Medical Dictionary for Regulatory Activities (MedDRA). Adverse events occurring between the signing of informed consent and administration of the first dose of randomized study medication will be regarded as pre-treatment AEs and included in the subject listings but not in the summary tables. Adverse events occurring after the first dose of randomized study medication will be defined as TEAEs.

The safety endpoints related to AEs are:

- Proportion of subjects with TEAEs.
- Proportion of subjects with treatment-related TEAEs.
- Incidence, type, and severity of the TEAEs after 30 weeks of study treatment.
- Incidence, type, and severity of the TEAEs after 52 weeks of study treatment.

The number and percentage of subjects with TEAEs will be summarized by study treatment group, overall, and by system organ class (SOC) and preferred term (PT) using frequency counts and percentages. The summaries will also include the number of TEAEs experienced. A similar summary will be produced for subjects with treatment-related TEAE.

The number and percentage of subjects with a TEAE that has a start date within 30 weeks of the start of treatment (≤ 182 days) will be summarized by severity and study treatment group, overall, and by SOC and PT using frequency counts and percentages. A similar summary will be produced including all TEAEs during the study (i.e., after 52 weeks of treatment).

If sufficient data exist, TEAE frequencies will be compared across treatment groups using Fisher's exact test or a similar test.

Additionally, the number and percentage of SAEs, TEAEs leading to discontinuation, and TEAEs related to the IP will be summarized by SOC, PT, and study treatment group. All AEs will be displayed in listings. AEs that occur during the run-in period will be summarized separately.

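### TEAEs are defined by onset alone, so a run-in adverse event that worsens on double-blind treatment can be missed by the primary safety tables unless the site happens to open a new record

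*SAP*

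**What the plan says.** Both documents give one timing rule. Protocol 13.7.2: "Adverse events occurring after the first dose of randomized study medication will be defined as TEAEs". SAP 12.2.2 repeats it almost word for word: "Adverse events occurring after the first dose of the randomized study medication will be defined as treatment-emergent adverse events (TEAEs". For events between consent and the first randomized dose, SAP 12.2.2 says they "will be regarded as pre-treatment AEs and will be included in the subject listings but not in the summary tables". Attribution to treatment also runs on onset: "Events will be assigned to the study treatment administered prior to the start of the TEAE". The 30-week summaries likewise select events by start date.

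The definition of an adverse event is wider. Protocol 12.4.1.1 covers any unfavourable "symptom or disease (new or exacerbated) temporally associated with the use of an IP, whether or not related to the IP". Among the things it says are not adverse events, it lists "Anticipated day-to-day fluctuations of pre-existing disease(s) or condition(s) present or detected at the start of the study that do not worsen". Protocol 12.4 requires abnormal safety assessments to be recorded as an AE or SAE, "including any that worsen from baseline, that is considered to be clinically significant in the medical and scientific judgment of the Investigator".

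The primary endpoints in SAP 4.1 include the proportion of subjects with TEAEs, the proportion with treatment-related TEAEs, and TEAE incidence, type and severity.

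**The concern.** Adverse events are collected from consent (Protocol 12.4.5), and every subject uses a placebo spray before randomization (Protocol 7.1). Some local events will therefore probably be open on the day of randomization. The randomization criteria (Protocol 9.3) exclude events that break the inclusion criteria and certain respiratory and ear infections. Nothing in them expressly excludes a subject with ongoing mild epistaxis or headache, and both are special-interest terms in SAP 12.2.3.

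Suppose mild epistaxis begins in the run-in and becomes moderate on double-blind spray. The preferred term does not change, so coding does not reveal a new event. If the site keeps one record, its start date precedes the first randomized dose and the event is pre-treatment. What is at stake is whether the primary safety endpoints count worsening on treatment consistently across sites. As written, that depends on site habit.

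**Working it through.** **Step 1. Set the rules side by side.**

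| Question | Where | Answer |
|---|---|---|
| What makes an AE a TEAE? | SAP 12.2.2, Protocol 13.7.2 | It occurs after the first randomized dose; worsening is not mentioned |
| Can an exacerbation be an AE? | Protocol 12.4.1.1, 12.4 | Yes |
| Does an AE that is already open get a new record when it worsens? | Protocol 12.4.5 | Not stated. Unresolved events are followed up, and the one updating instruction amends the existing record, to enter a diagnosis |
| What follows when an ENT finding worsens? | Protocol 11, 12.4.11 | Section 11 gives specialist referral; 12.4.11 captures clinically significant new findings as AEs |

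Two recording routes are therefore open to a site:

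- **New record at worsening.** The start date follows the first randomized dose, and the event enters the TEAE tables.
- **Severity updated on the run-in record.** The start date precedes the first randomized dose, and the event stays out of them.

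The documents do not choose between the two.

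**Step 2. Confirm the group size.** SAP 8.0 requires 300 subjects at 6 months with 25% attrition and 100 at one year with 50%: 300 / 0.75 = 400 and 100 / 0.50 = 200. The larger is 400, which reproduces the planned GSP 301 group. Each placebo group has 100. These sizes are used below only as multipliers.

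**Step 3. Illustrate the size.** The documents give neither the share of subjects with an AE ongoing at randomization (p) nor the share of those who worsen (w). Both are assumptions here, with p from 1% to 10% and w from 5% to 30%, and it is further assumed that no worsening is re-recorded. Subjects with an uncounted worsening = N × p × w.

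| p | w | GSP 301 (N = 400) | Each placebo arm (N = 100) | Percentage points |
|---|---|---|---|---|
| 1% | 5% | 0.2 | 0.05 | 0.05 |
| 1% | 30% | 1.2 | 0.3 | 0.3 |
| 5% | 15% | 3 | 0.75 | 0.75 |
| 10% | 15% | 6 | 1.5 | 1.5 |
| 10% | 30% | 12 | 3 | 3.0 |

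The last column is the most by which the proportion with any TEAE could fall. The true fall is smaller, because a subject with another TEAE during the 52 weeks is already counted. With the same p and w in every arm, the percentage is the same in every arm. A difference between arms needs a different w under GSP 301.

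**The case against.** The strongest reply is that an adverse event includes an exacerbation. A worsening on double-blind treatment can then be an event in its own right, occurring after dosing and so a TEAE. This stands in part. A reader might infer that every run-in event that worsens is bound to be missing from every TEAE table, and the documents do not support that. They do not settle the recording route, and an event re-recorded at worsening would be counted. But the definition says what qualifies as an event, not whether one already open receives a second record.

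A recording rule may also sit in the CRF completion guidelines that Protocol 12.4.9 mentions and that are not available here. The single start date and severity per row in listing shell L16.2.7.1 does not settle the matter, since separate records for worsened events would look the same.

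Third, such events are not invisible. Protocol 13.7.2 promises a separate summary of run-in AEs, and shell T14.1.9.5.19.1 gives it by arm with severity, relatedness and seriousness (SAP 12.2.2, which keeps pre-treatment events out of summary tables, needs reconciling with that). Nasal irritation and epistaxis grades are tabulated by arm at every visit in T14.1.9.10.1. SAP Table 2 also lists an SAE table apart from the treatment-emergent one, although the SAE tables in the Appendix 1 list of shells are all treatment-emergent. These outputs mitigate the gap. They do not correct the TEAE endpoints, and if severity is updated on a run-in record, the run-in summary would show a severity reached on double-blind treatment as a run-in finding. Headache and other non-nasal events have no counterpart to the ENT tables.

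Finally, the rule is the same in all arms. That is correct and limits the conclusion.

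**Conclusion.** The point stands as a gap in the definition behind the primary safety endpoints. Both documents use an onset-only rule, and a run-in event kept as one record that worsens on treatment falls outside the TEAE, severity, relatedness, special-interest and treatment-emergent SAE tables. Whether it is counted depends on a recording practice that the documents leave open.

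The size cannot be derived from the documents. On the assumed rates, with no re-recording, it runs from under 1 to about 12 of 400 GSP 301 subjects and from under 1 to 3 of 100 in each placebo arm. The effect on overall TEAE incidence is at most 3 percentage points and probably much less. It may matter more in sparse severity, SAE and special-interest rows, where a few events are visible, but nothing shows that the missed events would be mainly severe or serious: mild to moderate is also a worsening.

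A reader might also infer that the omission favours GSP 301. The documents give no evidence for a direction. A drug effect would be understated only if GSP 301 aggravates run-in events more than placebo does, and a long-term safety study should be able to detect that.

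**What to change.** In SAP 12.2.2, define a TEAE as an adverse event that starts on or after the first randomized dose, or one that started earlier and increases in severity or becomes serious after that dose. State that the second kind is counted with the date and severity of the worsening, so that the 30-week and 52-week tables place it correctly. List the change in SAP 1.0, because it departs from Protocol 13.7.2; Protocol 13 lets the SAP prevail where the two differ. At the blinded data review before database lock (SAP 10.0), check every AE ongoing at randomization for later worsening.

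The cost is a short SAP amendment, a small recording instruction to sites and a review of the AE records open at randomization. The recording instruction concerns AE collection (Protocol 12.4.5) as well as analysis, and the CRF has been final since 19 May 2016, so it is better given as completion guidance than as a form change. Where an existing record shows only one severity, the date of worsening may need a query to the site. The SAP can be changed without delay to the study, since Protocol 13 requires it to be final only before database lock.
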